## Purpose of the Study

To investigate whether the new applanation tonometer (Eye Check monitor) can provide intraocular pressure (IOP) measurements comparable to those of traditional tonometers such as the Goldmann applanation tonometer.

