The Goldmann applanation tonometer is the gold standard for measuring the IOP. It measures the force necessary to flatten (applanate) the central cornea. As shown in the figure, to perform a measurement the subject is seated in front of a slit-lamp microscope. The operator places a drop of fluorescent dye and anesthetic on the eye and asks the patient to look straight ahead, open both eyes wide, fix his/her gaze and keep perfectly still. The operator gently holds up the patient's top eyelid, taking care not to put any pressure on the eye and moves the tonometer forward and perpendicular to the cornea until the prism rests gently on the center of the subject's cornea. With the other hand, the operator turns the calibrated dial on the tonometer thereby increasing the force applied by the probe on the cornea. The operator continues to increase the force until the tear film at the periphery of the probe (seen as a fluorescent ring) reaches a preset diameter. The probe is then withdrawn from the eye and the value on the dial, corresponding to the force necessary to flatten the cornea (calibrated in mmHg units of IOP) is recorded in the notes. The calibration takes into account the force to deform the cornea when the IOP is absent and the opposite capillary force generated by the meniscus of fluid.

Despite the availability of self-tonometers and the proof of their clinical value, IOP monitoring by patients, in their own environment, has not been used widely. As stated in the Liang review, the economical hurdles have prevented the commercialization of this technology: the lack of reimbursement for the instrument cost (e.g. \$2150 for the iCare Home tonometer <https://www.howmuchisit.org/icare-tonometer-cost/>), the training of the patient and data processing has deterred clinicians from implementing IOP home monitoring in their routine clinical practice. The

experience so far indicates that, to be adopted clinically for IOP monitoring, a self-tonometer must be: usable by most patients, require no corneal anesthetic, safe, require no or minimal training by ophthalmologists' clinical staff and capable to yield values that correlate well with gold standard tonometry.

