The EYE Check Tonometer satisfies all the above-mentioned criteria necessary for practical large-scale implementation of home IOP monitoring. The instrument comprises of an optical head, a flexible arm and a power and control unit. The optical head is similar to the Goldmann tonometer. It is composed of an acrylic transparent probe connected internally to a force sensor and an optical monitor which monitors the contact of the probe with the cornea. In addition, it contains a light pattern for self-alignment.

In operation, the subjects, seated in front of a table on which the device is placed, move their head to center the visible pattern in the optical head by adjusting the flexible arm. An audible message informs them when their eye is aligned with the optical head. Upon confirmation of adequate centering, the subjects bring the cornea in contact with the probe by leaning towards the probe. The probe moves and activates the force sensor while the area of contact is recorded. When a preset safe pressure is registered, an audible signal informs the subject to lean back and the fixation light is turned off. The output of the force sensor and the optical monitor are sampled frequently and transmitted to a laptop computer (to be replaced by a smartphone in the future). Following the procedure, the IOP is derived and quality control assessments are performed.

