## Design & Procedures

Prospective consecutive series of 50 adult patients. Consecutive patients coming to the Duke Eye Center will be approached by a research coordinator for the possibility of participating in the study. Subjects will be screened based on the inclusion and exclusion criteria (Selection of Subjects section). Eligible and willing patients will be asked to sign the consent form for the study.

Participants will be assigned a unique code number. The key to this code will be in a locked key file with the principal investigator. Both eyes will be evaluated in this study. The user (patient) will then be informed by a skilled technician, who is experienced with use of the Eye Check tonometer, on how to use it by themselves.

The subject will perform a self-alignment procedure that trains for alignment and assesses the results. During this procedure, no contact will be made with the probe. The progress will be monitored and recorded. Only subjects who pass the alignment criteria will proceed to obtain IOP measurements. Prior to the instillation of any eye drops, five immediately consecutive readings will be obtained with the Eye Check tonometer. Each of these readings will be recorded in the Eye Check tonometer connected computer without any subject identifier other than the identification code. IOP measurements by a certified ophthalmic technician using the Goldmann Applanation tonometer, within 5 minutes after the use of the Eye Check tonometer will be performed. Other data such as age, pachymetry, refractive error, etc., will be recorded.

Patients will be provided with a questionnaire to assess comfort and ease of use.

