#### Data Analysis & Statistical Considerations

The IOP readings from the Eye Check tonometer and the Goldmann will be compared. The Goldmann measurements are typically considered the gold standard. Mean IOP and standard deviation of IOP measurements using the two devices will be assessed.

If needed, for correlation analyses, data such as age, pachymetry, refractive error, etc., will be obtained by the clinical investigators from the charts.

The data of the Eye Check tonometer, which, as mentioned above, does not contain any subject identification or IOP data, will be analyzed. The IOP, Standard of Measurement, number of successful readings, and performance scores will be derived.

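### Does measuring only patients who pass self-alignment, without a planned count of those who fail, undermine the Goldmann comparison?

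*Combined protocol and SAP*

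**What the plan says.** The Purpose section asks whether the new tonometer "can provide intraocular pressure (IOP) measurements comparable to those of traditional tonometers". Under Design & Procedures the order is fixed: eligibility and consent, instruction by a technician, a self-alignment exercise without contact, then measurement. Of the alignment exercise it says "The progress will be monitored and recorded", and then "Only subjects who pass the alignment criteria will proceed to obtain IOP measurements". Goldmann tonometry is timed to within 5 minutes after the Eye Check readings, so study pairs come only from patients who passed. The same section notes "Both eyes will be evaluated in this study".

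The Data Analysis & Statistical Considerations section compares the two devices by mean and standard deviation. Its derived outputs end with "number of successful readings, and performance scores will be derived". It does not define the performance scores, name an analysis population, or list a count of patients who did not pass.

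The Background & Significance section sets adoption requirements, among them that "a self-tonometer must be: usable by most patients", and then asserts: "The EYE Check Tonometer satisfies all the above-mentioned criteria". It also describes normal operation: "Upon confirmation of adequate centering, the subjects bring the cornea in contact with the probe".

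**The concern.** Patients are selected after consent and before any reading, by a test of the skill that the device demands. Everything in the analysis section then describes the selected group, and nothing there says so. A reader given only the comparison would not know whether it represented 50 of 50 patients or, say, 40 of 50.

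Two things appear to be at stake. One is the population to which the Goldmann comparison applies. The other is usability. The background makes use by most patients a condition of adoption, and centring is part of ordinary operation, so an alignment failure is evidence about the device. If those failures dropped out of sight and someone formed a success rate over passers, that rate would look better than the experience of everyone who tried.

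**Working it through.** **Inputs.** The documents give one relevant number, enrolment of about 50 (Design & Procedures; Subject Recruitment). It comes without a derivation, so there is no sample-size figure to reproduce. They give no expected pass rate. The pass rates and success rates below are assumptions, shown as a range.

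**1. Effect on the planned comparison.** Take one pair per patient and express precision in standard deviations (SD) of the paired difference. The approximate 95% half-width for one limit of agreement is 1.96 × √(1/n + 1.96²/(2(n − 1))). The half-width for the mean difference is 1.96/√n.

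| Assumed pass rate | Patients with pairs | Mean difference, half-width (SD) | Limit of agreement, half-width (SD) | Exact 95% CI for the pass rate |
|---|---|---|---|---|
| 100% | 50 | 0.28 | 0.48 | 92.9–100% |
| 90% | 45 | 0.29 | 0.50 | 78.2–96.7% |
| 80% | 40 | 0.31 | 0.53 | 66.3–90.0% |
| 70% | 35 | 0.33 | 0.57 | 55.4–82.1% |
| 60% | 30 | 0.36 | 0.62 | 45.2–73.6% |

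For example, at n = 40: 1.96 × √(0.0250 + 0.0493) = 0.53. At n = 50: 1.96 × √(0.0200 + 0.0392) = 0.48. The difference is about 0.05 to 0.06 SD. Failures widen the intervals modestly and do not shift the estimate of agreement among passers.

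**2. Effect on a usability rate, if one were formed.** Let s be the proportion of passers who obtain usable readings and p the pass rate. A rate over passers is s, the rate over all who attempt alignment is s × p, and the gap is s × (1 − p). With s = 90% assumed:

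- p = 100%: 90%, gap 0
- p = 90%: 81%, gap 9 points
- p = 80%: 72%, gap 18 points

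At p = 80%, 36/40 = 90% (exact 95% CI 76.3–97.2%) becomes 36/50 = 72% (57.5–83.8%).

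**3. Would that reverse a conclusion?** Read most patients as more than half, which is also an assumption. The exact lower limit is 51.2% at 33/50 and 49.2% at 32/50, so the conclusion changes at 32 or fewer successes. The fewest alignment failures that reach this point, with successes rounded to whole patients, are:

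- s = 100%: 50 − 32 = 18 failures
- s = 90%: 14 failures (36 passers × 0.9 = 32.4, so 32)
- s = 80%: 10 failures (40 passers × 0.8 = 32)

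Between 20% and 36% of patients would have to fail alignment.

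**4. Is either quantity in steps 2 and 3 planned?** No. The analysis section promises a number of successful readings, not a proportion of patients, and the Purpose section contains no usability hypothesis. Steps 2 and 3 therefore measure an error that someone would have to introduce later.

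**The case for a change.** The best argument for a change is that recording is not reporting. The protocol captures alignment progress but ties it to no output, and an undefined performance score commits nobody to a denominator. The exclusion criteria already remove patients with tremor, upper-extremity arthritis, poor acuity or expected inability to comply, so alignment is a second filter on a population already chosen for dexterity. The background claims usability outright, and this study will generate evidence on that claim. A line of flow counts would cost little.

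Most of this is true, and part of it stands. A report without the numbers consented, attempting alignment and passing would be incomplete. The plan also leaves open whether passing is judged per eye or per patient, which the report must state because both eyes are evaluated. But these are reporting details that a competent analyst would be expected to supply, and the protocol already shows that only passers are measured.

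The argument does not carry over to a formal usability endpoint. That would need a definition of usable readings, and the plan does not say whether the five readings are per eye or per patient. A comparison of non-passers with passers would need age and refractive error for patients who were never measured; the recorded alignment progress does not supply these, and chart data are to be taken only if needed. Both would enlarge the study's aims rather than repair its analysis.

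**Conclusion.** The observation is accurate: only passers are measured, and the analysis section neither counts the others nor labels the comparison as conditional on passing. It does not call for a change. Followed as written, the plan gives no wrong result for its stated purpose. Agreement between two tonometers can be assessed only where both give a reading, and in normal use contact follows confirmed centring, so restricting to passers fits the question. The study's own pass criteria are not given and may be stricter or looser than that operating step. This limits what a failure says about usability, but it does not invalidate agreement among those measured.

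The cost to the planned comparison is some precision: 0.48 to 0.53 SD for a limit of agreement at an assumed 80% pass rate, with one pair per patient. The 9- and 18-point gaps apply to a rate that the plan does not contain, and they rest on assumed pass and success rates.

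This is a gap that sensible analysts fill in reporting. They would give the flow counts, say that the comparison covers patients who passed, and use everyone who attempted alignment as the denominator if they quote a patient-level success rate. The judgement assumes that the recorded alignment progress identifies who attempted and who passed, as the protocol's wording suggests.

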### Selection of Subjects

#### Inclusion criteria:

Age of 18 years or older,  
Any glaucoma patient or glaucoma suspect patient

#### Exclusion criteria:

Arthritis affecting the upper extremity in the patient or caregiver  
Patient unwilling or assessed to be unable to comply with the study protocol  
Any corneal abnormalities such as opacities, scars, Fuchs dystrophy, map dot fingerprint dystrophy, history of recurrent corneal abrasion, corneal surgery such as Lasik, PRK, DSAEK, transplant or implant  
History of any ongoing ocular symptoms such as eye pain or redness or discharge  
History of recent ocular surgery (done in the past 3 months)  
History of any filtering or tube surgery for glaucoma (to reduce risk of infection associated complications)  
Recent eye infection (within the past 3 months)  
History of diabetes for > 5 years duration  
Monocular patient  
Best corrected visual acuity < 20/70  
Head or hand tremors

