### Subject Recruitment

Patients will be recruited from the glaucoma clinic who are already scheduled for a standard of care visit. Someone known to them will introduce the study to them and if interested a member of the study team will review the study and obtain consent before any study procedures are done. Approximately 50 subjects will be enrolled in this study.

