### Risk/Benefit Assessment

Risks: It is possible that the patient may abrade the cornea during a measurement resulting in a corneal abrasion. The likelihood of such an event occurring with the Eye Check tonometer is remote due to the disposable probe cover made out of contact lens material (thus protecting the cornea) during the measurement. Pain, redness, watering, and blurry vision are symptoms that would alert the patient immediately and they will be instructed to contact the principal investigator and stop the study. Such abrasions typically heal within 24-48 hours unless the patient is a diabetic in whom it may take longer and thus a history of diabetes is an exclusion factor. There is a remote possibility that the corneal abrasion can get infected.

Sanitation of device - The head of the unit will be bent so that the entire tip will be dipped in the standard cleaning solutions (those used for Goldmann tonometer tips), then dried (per the current

protocol), and then used on any subsequent patient in the study. The actual device will be wiped down with cavi wipe per standard clinic protocols.

Benefits: The physician will be able to assess the accuracy of the IOP measurements with the Eye Check tonometer, which has the potential to be used as a device by which the patients can check their own IOP at home in the future. This may lead to better management of their glaucoma.

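### The risk section treats any history of diabetes as an exclusion, but the eligibility list excludes only diabetes of more than 5 years

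*Combined protocol and SAP*

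**What the plan says.** Diabetes is mentioned in two places in the combined protocol and SAP.

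- **Selection of Subjects, Exclusion criteria:** one item reads "History of diabetes for > 5 years duration".
- **Risk/Benefit Assessment:** after giving the usual healing time of a corneal abrasion as 24-48 hours, the text continues "unless the patient is a diabetic in whom it may take longer and thus a history of diabetes is an exclusion factor". No duration is given.

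Two further statements show which text governs entry. Design & Procedures states "Subjects will be screened based on the inclusion and exclusion criteria (Selection of Subjects section"), so the listed criteria are the operative ones. The Inclusion criteria, beyond an age of 18 years or older, admit "Any glaucoma patient or glaucoma suspect patient" and do not restrict on diabetes. Planned enrolment, under Subject Recruitment, is about 50.

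**The concern.** The risk section gives a reason for excluding diabetics (slower healing of an abrasion) and states it for diabetics in general. The list that decides enrolment removes only those with longer-standing disease. Patients with diabetes of 5 years or less fall between the two: the stated reason covers them, the operative criterion does not.

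What is at stake is the accuracy of a safety statement. Corneal abrasion is the first risk the protocol names, and participants bring their own cornea against the probe for five consecutive readings, with both eyes evaluated. Excluding diabetics is the only measure the risk section ties to delayed healing; the probe cover bears on how likely an abrasion is, and the symptom instructions on noticing one. Someone weighing the risks from that section would conclude that no diabetics take part, which the eligibility list does not ensure.

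**Working it through.** The point is one of consistency. The plan states no figure to reproduce, and the conclusion depends on no calculation.

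**Comparison of the texts**

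| Patient | Exclusion criteria (operative) | Risk/Benefit Assessment |
|---|---|---|
| No diabetes | Not excluded on this ground | Not excluded on this ground |
| Diabetes, 5 years or less | Not excluded on this ground | Described as excluded |
| Diabetes, more than 5 years | Excluded | Described as excluded |

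1. Screening follows the Selection of Subjects section, so the middle column decides entry.
2. No other item in the inclusion or exclusion criteria mentions diabetes, so nothing else removes the middle row as a group.
3. No section gives a reason for the 5-year limit or carries it into the risk statement.
4. The two descriptions therefore differ by exactly the middle row.

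**Illustration of size (assumed inputs)**

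The documents give neither the prevalence nor the duration of diabetes in this clinic. Let *p* be the share of otherwise eligible patients who have diabetes, and *f* the fraction of those who have had it for 5 years or less. Both are assumptions; only N = 50 comes from the protocol (Subject Recruitment). Because longer-duration diabetics are screened out before enrolment, the share of enrolled patients in the gap is

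share = *p* × *f* / (1 − *p* × (1 − *f*))

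For *f* = 1/3:

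- *p* = 0.10: 0.0333 / 0.9333 = 0.0357; × 50 = 1.8
- *p* = 0.25: 0.0833 / 0.8333 = 0.100; × 50 = 5.0

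Varying *f*:

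| *f* | *p* = 0.10 | *p* = 0.25 |
|---|---|---|
| 0.20 | 0.020 / 0.920 × 50 = 1.1 | 0.050 / 0.800 × 50 = 3.1 |
| 1/3 | 1.8 | 5.0 |
| 0.50 | 0.050 / 0.950 × 50 = 2.6 | 0.125 / 0.875 × 50 = 7.1 |

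The range is about 2 to 5 of 50 with *f* at one third, and about 1 to 7 of 50 across the whole grid. These count enrolled patients. The number exposed to the probe could be lower, because only those who pass the contact-free alignment step go on to measurement.

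**The case against.** The strongest reply is that the risk section is shorthand. It opens with the same phrase as the list item, explains why diabetes appears on the list, and need not be read as a second, wider rule. On that reading nothing conflicts: screeners are sent to one list, and that list is clear. This is plausible, and it may well be how the mismatch arose. It does not remove it. The risk section links the exclusion to slower healing in diabetics generally, and that reason applies equally to the patients the list admits. Even as shorthand, the text presents as removed a risk that is only partly removed.

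Other points on that side stand in whole or in part:

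- **Weight.** The protocol calls abrasion remote. The probe cover, the symptom instructions and adverse event reporting protect everyone enrolled. A lower rating would be defensible.
- **Screening.** It is true that the plan already names one governing list. The defect is that the safety rationale does not match it.
- **Counts.** It is true that they rest on assumed inputs and that the point does not need them. They show only that the group need not be empty.
- **Reason for the limit.** Other thresholds in the list, such as the 3-month windows and the visual acuity cut-off, also carry no reason. A missing reason is not itself a contradiction; it matters here only because the risk section offers a reason that does not stop at 5 years.

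**Conclusion.** The concern holds. The risk section and the operative eligibility list describe different excluded groups, and the difference is patients with diabetes of 5 years or less. The protocol allows these patients to be enrolled; this does not show that any were.

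The conclusion rests on the wording alone. The size, about 2 to 5 of 50 and at the widest about 1 to 7, rests on an assumed diabetes prevalence of 10% to 25% and an assumed short-duration fraction of one third (varied from 20% to 50%). It counts patients, not injuries.

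The importance is modest. The comparison of the two tonometers, its endpoints and its analysis are untouched. It should still be corrected, because a stated protection ought to match the criteria that deliver it. The consent pages were not available for review, so nothing is concluded about what participants are told.

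**What to change.** Reconcile the diabetes item in the Exclusion criteria with the diabetes sentence in the Risk/Benefit Assessment, so that the criterion and its justification describe the same group. Which text changes is for the investigators and the IRB; no view is taken here on which rule is right. If a duration limit is kept, the risk section should state it and give the reason for it. Screening should then use the reconciled wording.

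The cost is a one-line amendment. Depending on the choice made, either a few patients become ineligible or the risk text becomes slightly less reassuring.

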### Subject Recruitment

Patients will be recruited from the glaucoma clinic who are already scheduled for a standard of care visit. Someone known to them will introduce the study to them and if interested a member of the study team will review the study and obtain consent before any study procedures are done. Approximately 50 subjects will be enrolled in this study.

